Aim 3: We will use logistic regression models to assess the utility of presence/absence of CAMLs after accounting for clinical factors and nodule characteristics. The primary analysis will be at the patient level, since this approach is most consistent with the potential future application of a validated CAML test in the clinic. The dependent variable will be a binary indicator of patient disease status as described for Aim 2 (1=diseased, 0=disease free). Independent variables will include presence/absence of CAMLs as well as factors previously identified in the literature as important predictors of lung cancer status including age, gender, smoking status, lesion diameter, spiculation, family history of lung cancer, emphysema, clear borders, and exposure to asbestos or other common pulmonary carcinogens.^{xv xvi xvii} When more than one lesion is detected in the same patient, lesion-specific covariate values (e.g., nodule diameter, spiculation) for that patient will be based on the nodule with highest risk of lung cancer. Continuous covariates may be modelled using restricted cubic splines to account for non-linear effects. As recommended by Pepe et al, Seshan et al and Vickers et al, the significance of the association between CAML test results and cancer status controlling for previously established clinical and radiological characteristics will be assessed using a Wald statistic from the multivariable logistic regression model (two-sided, 5% type I error).^{xviii xix} Table 2 displays detectable differences between CAML+ and CAML- patients from these multivariable^{xx}models, under a number of conditions.^{xxi} These estimates assume data are available from 1,000 patients with suspicious nodules (35 CAML+ and 965 CAML-), and approximately 3.5% of patients will subsequently have biopsy-confirmed lung cancer.

Table 2. Detectable differences in proportion with lung cancer between CAML+ and CAML – patients.

Squared multiple correlation between CAML status and other independent variables in the model	Detectable difference in the proportion with lung cancer between CAML+ and CAML – patients	Power
0.0	0.111	80%
0.1	0.118	80%
0.2	0.127	80%
0.3	0.138	80%

Table 3. Two-sided 95% confidence intervals for varied AUCs

AUC	Lower Bound	Upper Bound
0.80	0.71	0.89
0.85	0.77	0.93
0.90	0.83	0.97

0.95	0.90	1.00
------	------	------

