Receiver Operating Characteristic (ROC) curves and area under the ROC curve (AUC), with associated 95% two-sided confidence intervals, will be created to summarize the predictive accuracy of the model. Given the anticipated sample size, the upper and lower bounds for 95% two-sided confidence intervals for a range of possible AUCs are presented in Table 3.^{xxii} In addition, the performance of the model will be evaluated using leave-one-out cross validation.

In secondary analyses, we will test second-order interactions between presence/absence of CAMLs and other covariates to explore whether test performance differs among subsets of the population defined by demographic, clinical and nodule characteristics.

In exploratory analyses we will conduct nodule-specific analyses using methods similar to those described above. In this case, the dependent variable will be a binary indicator of nodule disease status (1=cancer detected, 0=cancer not detected). To account for the fact that some subjects may have multiple nodules, the logistic models will be fit using generalized estimating equation methods (GEE) (and robust variance estimates will be used for inference.^{xxiii} The power estimates in Table 2 are based on the assumption that there will be only 1 nodule per patient. Given that some subjects will have multiple nodules, the actual power of these exploratory analyses will likely exceed the stated estimates.

We will also evaluate the value of adding CAMLs to previously defined algorithms for evaluation of pulmonary nodules and the ability of CAMLs to potentially replace other known variables.

Trial feasibility: The trial calls for a total of 1000 evaluable patients accrued over 2 years. To assess the feasibility of this accrual rate, we examined the number of potentially eligible patients seen in the FCCC pulmonary clinic for FY 2017 (7/1/2016 to 6/30/2017). We found that there were over 1200 patients referred for evaluation of pulmonary nodules. The exact size of these nodules has not been captured in the data base, but the majority are within the indeterminate range. At the VA Philadelphia, the pulmonary nodule clinic performs over 1500 bronchoscopies/year and sees over 200 patients/year with pulmonary nodules measuring .8-3.0 cm. Therefore, between the two institutions, we feel confident that we will be able to enroll 1000 patients with indeterminate nodules within 24 months of activation.

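### Nodule-level GEE analysis: the robust-variance Wald test of CAML breaks down when no CAML+ patient has cancer, and the plan has no rule for that case

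*Combined protocol and SAP*

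**What the plan says.** All of this is in Section 9.0 (Statistical Considerations) of the combined protocol and SAP, under Aim 3.

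- **Patient-level analysis, labelled primary.** The association of CAML with cancer, adjusted for clinical and radiological factors, "will be assessed using a Wald statistic from the multivariable logistic regression model (two-sided, 5% type I error"). No robust variance is mentioned here.
- **Planning inputs.** There are 1,000 patients, of whom 35 are CAML+ and 965 CAML-, and "approximately 3.5% of patients will subsequently have biopsy-confirmed lung cancer".
- **Nodule-level analysis.** "In exploratory analyses we will conduct nodule-specific analyses using methods similar to those described above". Here "the dependent variable will be a binary indicator of nodule disease status (1=cancer detected, 0=cancer not detected"). Because a patient may contribute several nodules, "the logistic models will be fit using generalized estimating equation methods (GEE) (and robust variance estimates will be used for inference".

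The section remarks that the power of the nodule-level analysis should be above that in Table 2. It says nothing about the type I error of that analysis. It names no fallback (exact, likelihood-ratio, penalised or permutation) for the case where a CAML-by-cancer cell is empty.

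**The concern.** CAML status belongs to the patient, so all nodules of one patient share it. With 35 CAML+ patients and 3.5% cancer, an uninformative test yields on average 35 × 0.035 = 1.2 cancers among CAML+ patients. A count of zero is therefore common.

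With zero events the CAML+ fitted risk goes to 0 (separation). A model-based standard error then becomes enormous and the Wald test does not reject. The robust variance is built from observed residuals. These vanish along with the fitted risk, so the robust standard error stays small while the estimate runs off towards minus infinity. The Wald test rejects in every such sample.

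At stake is a nodule-level report with a p-value near 0 saying that CAML+ nodules are protected from cancer, when the data hold no such evidence and the patient-level test on the same patients shows nothing.

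**Working it through.** **Inputs from Section 9.0:** n1 = 35 CAML+, n0 = 965 CAML-, cancer risk 0.035, two-sided 5% Wald test, robust variance at nodule level.

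**1. The plan's own figure.** Table 2 reproduces with the cited sample-size method for logistic regression with a binary covariate:

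N = [1.96·√(P(1−P)/B) + 0.842·√(p0(1−p0) + p1(1−p1)(1−B)/B)]² / [(p1−p0)²(1−B)(1−R²)], with B = P = 0.035.

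For the difference 0.111 at R² = 0: p0 = 0.035 − 0.035 × 0.111 = 0.0311, p1 = 0.1421, N = 1,016. The other three rows give 1,016, 1,008 and 999. Table 2 is sound as a patient-level power statement, so the inputs are being read as the plan intends.

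**2. Chance of an empty cell under no association.** 0.965^35 = 0.287. Extra nodules do not change this, because it is fixed by whether any CAML+ patient has cancer.

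**3. Robust variance in an empty cell** (one nodule per patient). With fitted risk p and q = 1 − p, the CAML+ log-odds has robust variance n1·p² / (n1·p·q)² = 1/(n1·q²), which tends to 1/35 (SE 0.169) as p goes to 0. For 34/965 in the CAML- group the variance is 1/34 + 1/931 = 0.0305. The SE of the contrast is √(0.0286 + 0.0305) = 0.243.

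**4. Check by fitting 0/35 against 34/965.**

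| Method | Result |
|---|---|
| GEE, robust | coefficient −21.3, SE 0.243, p about 0 |
| GEE, bias-reduced robust | SE 0.247 |
| Model-based Wald | SE 36,511, p = 0.9995 |
| Likelihood ratio | chi-square 2.47, p about 0.12 |

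The fit reported convergence, so that flag would not warn the analyst.

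**5. Type I error, exact enumeration of the two binomials, one nodule per patient.**

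- Empty-cell rejections: 28.7 points
- Upper-tail rejections: 3.6 points
- Robust Wald total: 32.4% (before rounding of the parts)
- Model-based Wald: 3.6%
- Fisher's exact test: 2.6%

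In this unadjusted case the robust and model-based variances coincide whenever neither group has an empty cell. The whole gap therefore comes from the empty cell.

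**6. Simulated null, robust Wald, 4,000 runs each** (nodule counts of 60/20/10/6/4% for 1 to 5 nodules and the covariate effects are assumptions): 32.6% with one nodule and no covariates; 32.1% with one nodule and covariates; 33.3% with 1–5 nodules and no covariates; 32.0% with 1–5 nodules and covariates.

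**7. Dependence on the inputs (exact, no association).**

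| CAML+ of 1,000 | Cancer risk | Robust Wald size |
|---|---|---|
| 35 | 3.5% | 32.4% |
| 50 | 3.5% | 20% |
| 100 | 3.5% | 5.9% |
| 180 | 3.5% | 3.5% |
| 35 | 5% | 20% |
| 35 | 10% | 5.7% |

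**8. If CAML does carry information.** The chance of an empty cell is 0.95^35 = 17% at a CAML+ risk of 5%, 0.93^35 = 8% at 7%, and 0.858^35 = 0.5% at the 14.2% implied by Table 2.

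**9. Candidate remedies under the null** (nodule counts and second-malignancy rates assumed). Withholding the robust p-value when the cell is empty gave a size of 3.3% to 3.7% in every setting. Replacing robust GEE by a nodule-level Firth model gave 5.5% to 14.8% once cancer patients could have a second malignant nodule. A robust score test still rejected 27% to 30% of the time.

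**The case against.** The case for leaving this alone has four parts.

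- **The analysis is exploratory.** This stands. The 5% level is attached to the patient-level test, and the nodule-level analysis inherits it only through a statement that its methods are similar.
- **The failure would be visible.** Largely true. An odds ratio near zero is conspicuous, and Aim 2 already requires PPV and sensitivity on the same patients, which would show 0/35 and 0%. But the software returns a confident p-value, and the plan gives the analyst no ground for setting it aside.
- **There may be far more than 35 CAML+ patients.** The background (Section 1.1) reports 18% positivity in benign lung disease, or about 180 in 1,000 mostly benign patients, and there the defect is gone. It also shrinks if CAML status is correlated with other risk factors: two such simulated scenarios gave 12.8% and 7.1%. This limits the size of the problem, but 35 is the figure the plan itself uses.
- **Robust variance is the standard way to handle several nodules per patient.** This stands, and it argues for keeping robust GEE.

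A reader might infer more than the documents support:

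- **That the main Aim 3 result is compromised.** No robust variance is specified for the patient-level test, and with model-based variance its size is about 3.6%.
- **That a useless test would be endorsed one time in three.** False support is about 3.6 points; the rest point the other way.
- **That the CAML interaction tests are affected.** They are listed as secondary analyses before GEE is introduced, and no robust variance is assigned to them.
- **That the fault is only that the Wald variance is not evaluated under the null.** The robust score test fails too. The cause is separation combined with an empirical variance.

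**Conclusion.** The point holds as a gap in an exploratory analysis. Followed as written at the plan's own inputs, the nodule-level robust Wald test of CAML has a two-sided type I error of about 32%, of which 28.7 points come from samples with no cancer among CAML+ patients. The result rests on 35 CAML+ patients, 3.5% cancer, no association between the two, and the two-sided 5% Wald test carrying over to the nodule level. It was not sensitive to the nodule counts and covariate effects tried in step 6. It is sensitive to the number of CAML+ patients and to cancer prevalence, and is close to nominal at about 100 CAML+ or 10% cancer. The amendment is worth making because it is cheap and prevents a spurious protective finding, but it does not touch the primary patient-level conclusion.

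**What to change.** Keep GEE with robust variance. Add to the nodule-specific paragraph of Section 9.0 wording such as: *If any cell of the CAML-by-cancer table is empty, no robust-variance p-value or confidence interval will be reported for the CAML effect. The cell counts will be given, and inference on CAML will be taken from a patient-level method: an exact test, a penalised likelihood-ratio test, or a permutation of CAML status across patients.* Name one of the three in advance.

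Do not replace robust GEE throughout with a nodule-level Firth model. It ignores the clustering that GEE was chosen to handle, with the loss of size control shown in step 9. A bias-reduced robust variance or a robust score test does not solve the problem either.

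The cost is one or two sentences, with standard software and no extra patients or data. The only loss is that empty-cell samples will have no nodule-level robust p-value.

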10.0 Data and Safety Monitoring Plan

10.1 Monitoring Plan

This study does not involve any intervention, thereby posing minimal risk to the patient. The patient's visit will be as needed for standard of care and no visit is needed specifically for this study. Therefore, sponsor investigator will be responsible for conduct of the study. Investigator sponsored research unit (ISRU) will be conducting spot check of the study to ensure timely entry of patient and related study data.

10.2 Data & Safety Monitoring Board (DSMB)

The study is purely observational with no interventions. It does not involve more than minimal risk to the patients, and will not be reviewed by DSMB.

11.0 Administrative

This study will be conducted in accordance with local, state and Federal regulations and according to accepted good clinical practice guidelines.

11.1 Data Reporting

Patients will be registered in OnCore and patient data will be entered at each site in electric case report forms in electronic data capture system RedCap that will be password protected. The FCCC Study Monitor will request case report forms to be completed within 2 weeks of the protocol visit. Participating sites are responsible to respond to queries prior to the next scheduled monitoring visit.

All patient information will be stored in an EDC system accessible only to the study team members for the purpose of entering, reviewing and analyzing data. Any paper records, such as case report files, produced will be stored in a secure location. Confidentiality of the patient data will be maintained at all time.

Patients registered in the trial will be assigned a registration number. If needed, data will transferred in a de-identified manner between institutional encrypted emails only.

11.2 Retention of Records

All the study related records will be collected form the participating sites as per contract and retained at Fox Chase Cancer Center for 3 years after the trial ends.

11.3 Informed Consent

The IRB approved informed consent documents must be signed by the patient, or the patient's legally authorized representative, before his or her participation in the study. The case history for each patient shall document that informed consent was obtained prior to participation in the study. A copy of the informed consent documents must be provided to the patient or the patient's legally authorized representative. If applicable, they will be provided in a certified translation of the local language.

Original signed consent forms must be filed in each patient's study file or medical record with a copy in the study file.

Number of years since last use:

(# of years) _____

Exposures:Asbestos exposure: No YesOccupational (specify)
_____Hobby (specify)
_____Residential (specify)
_____Random exposure: No YesIf yes, specify:
_____Agent Orange: No YesOther Occupational Exposure: No Yes

Confidential

Page 3 of 7

Medical History:

Family History:

- Lung cancer
- Head and Neck Cancer
- Bladder Cancer
- Esophageal Cancer
- Other (specify) _____

Other cancer, please specify: _____

Personal Medical History:

- COPD
- Reactive airways disease
- CAD
- Other pulmonary disease
- History of pneumonia

Height (cm): _____

((cm))

Weight (Kg): _____

((Kg))

Calculated BMI: _____

Pulmonary Function Tests

FEV1 (liters) _____

((liters))

FEV1 (% pred) _____

((% pred))

FEV1/FVC _____

DLCO _____

((numeric field))

DLCO % Predicted _____

((% pred))

Confidential

Page 4 of 7

Scan:

Date of Scan: _____

Characteristics of Nodule(s):

Nodule 1

- RUL
- RML
- RLL
- LUL
- LLL
- Lingula

Location:

Solid Semisolid

Size (cm):

((cm)) _____

Contour

- Smooth
- Spiculated
- Ground glass

If nodule is part solid/ground glass: % solid.

(% solid) _____

Calcification

- Not present
- Diffuse
- Central
- Laminated
- Popcorn
- Present, Not otherwise specified

Fat

Not present Present

Satellite nodules

Not present Present

Do you need to add another Nodule?

Yes No

Nodule 2

- RUL
- RML
- RLL
- LUL
- LLL
- Lingula

Location:

Solid Semisolid

Size (cm):

((cm)) _____

Contour

- Smooth
- Spiculated
- Ground glass

Confidential

Page 5 of 7

If nodule is part solid/ground glass: % solid.

(% solid)

Calcification

- Not present
- Diffuse
- Central
- Laminated
- Popcorn
- Present, Not otherwise specified

Fat

- Not present
- Present

Satellite nodules

- Not present
- Present

Do you need to add another Nodule?

- Yes
- No

Nodule 3

 RUL RML RLL LUL LLL Lingula

Location:

 Solid Semisolid

Size (cm):

((cm))

Contour

 Smooth Spiculated Ground glass

If nodule is part solid/ground glass: % solid.

(% solid)

Calcification

- Not present
- Diffuse
- Central
- Laminated
- Popcorn
- Present, Not otherwise specified

Fat

- Not present
- Present

Satellite nodules

- Not present
- Present

Do you need to add another Nodule?

- Yes
- No

Nodule 4

 RUL RML RLL LUL LLL Lingula

Confidential

Page 6 of 7

Density:	 Solid  Semisolid
Size (cm):	----- (cm))
Contour	 Smooth  Spiculated  Ground glass
If nodule is part solid/ground glass: % solid.	
----- (% solid)	
Calcification	 Not present  Diffuse  Central  Laminated  Popcorn  Present, Not otherwise specified
Fat	 Not present  Present
Satellite nodules	 Not present  Present
Do you need to add another Nodule?	
 Yes  No	
Nodule 5	 RUL  RML  RLL  LUL  LLL  Lingula
Location:	
Density:	 Solid  Semisolid
Size (cm):	----- (cm))
Contour	 Smooth  Spiculated  Ground glass
If nodule is part solid/ground glass: % solid.	
----- (% solid)	
Calcification	 Not present  Diffuse  Central  Laminated  Popcorn  Present, Not otherwise specified
Fat	 Not present  Present
Satellite nodules	 Not present  Present

Confidential

Page 7 of 7

CAML (Cancer-Associated Macrophage-Like Cells) testing results:

CAML Date: _____

CAML cells present?

 Present Absent

CAML size

(microns) _____

CAML number

(numeric field) _____

CAML Comments

(free text field) _____

CTCs present?

 Present Absent

CTC number

(numeric field) _____

Apoptotic CTC

(numeric field) _____

EMT CTC

(numeric field) _____

CEVC present?

 Present Absent

CEVC number

(numeric field) _____

FOLLOW UP FORM

Confidential

Follow Up Form

Record ID

Date

Institution

 FCCC VA

Cigarettes:

 Never Active Quit since last time

Peak use (packs per day):

 < 0.25 0.25 0.50 0.75 1.00 1.25 1.50 1.75 2.00
 >2.00

Age at last use:

Number of years since last use:

(# of years)

Medical History:Family History: Change since last visit? Yes No

Family History:

- Lung cancer
- Head and Neck cancer
- Bladder cancer
- Esophageal cancer
- Other

Other cancer, please specify:

Personal Medical History: Change since last visit? Yes No

Personal Medical History:

- COPD
- Reactive airways disease
- CAD
- Other pulmonary disease
- History of pneumonia

Height (cm):

((cm))

Weight (Kg):

((Kg))

Confidential

Page 2 of 6

Calculated BMI _____

Pulmonary Function Tests

FEV1 (liters) _____

(liters) _____

FEV1 (% pred) _____

(% pred) _____

FEV1/FVC _____

DLCO _____

(numeric field) _____

DLCO % Predicted _____

(% pred) _____

Scan:

Date of Scan _____

Characteristics of Nodule(s):

Nodule 1: _____

 RUL RML RLL LUL LLL Lingula

Location: _____

 Solid Semisolid

Density: _____

((cm)) _____

Size (cm): _____

 Smooth Spiculated Ground glass

Contour: _____

If nodule is part solid/ground glass: % solid. _____

(% solid) _____

Confidential

Page 3 of 6

Calcification	 Not present  Diffuse  Central  Laminated  Popcorn  Present, Not otherwise specified
Fat	 Not present  Present
Satellite nodules	 Not present  Present
Do you need to add another Nodule?	 Yes  No
Nodule 2	 RUL  RML  RLL  LUL  LLL  Lingula
Location:	
Density:	 Solid  Semisolid
Size (cm):	_____ (cm))
Contour:	 Smooth  Spiculated  Ground glass
If nodule is part solid/ground glass: % solid.	_____ (% solid)
Calcification	 Not present  Diffuse  Central  Laminated  Popcorn  Present, Not otherwise specified
Fat	 Not present  Present
Satellite nodules	 Not present  Present
Do you need to add another Nodule?	 Yes  No
Nodule 3	 RUL  RML  RLL  LUL  LLL  Lingula
Location:	
Density:	 Solid  Semisolid

Confidential

Page 4 of 6

Size (cm):

((cm))

Contour:

 Smooth Spiculated
 Ground glass

If nodule is part solid/ground glass: % solid.

(% solid)

Calcification

 Not present
 Diffuse
 Central
 Laminated
 Popcorn
 Present, Not otherwise specified

Fat

 Not present Present

Satellite nodules

 Not present Present

Do you need to add another Nodule?

 Yes No

Nodule 4

 RUL
 RML
 RLL
 LUL
 LLL
 Lingula

Density:

 Solid Semisolid

Size (cm):

((cm))

Contour:

 Smooth Spiculated
 Ground glass

If nodule is part solid/ground glass: % solid.

(% solid)

Calcification

 Not present
 Diffuse
 Central
 Laminated
 Popcorn
 Present, Not otherwise specified

Fat

 Not present Present

Satellite nodules

 Not present Present

Do you need to add another Nodule?

 Yes No

Confidential

Page 5 of 6

Nodule 5	 RUL  RML  RLL  LUL  LLL  Lingula
Location:	
Density:	 Solid  Semisolid
Size (cm):	----- (cm))
Contour:	 Smooth  Spiculated  Ground glass
If nodule is part solid/ground glass: % solid.	
	----- (% solid)
Calcification	 Not present  Diffuse  Central  Laminated  Popcorn  Present, Not otherwise specified
Fat	 Not present  Present
Satellite nodules	 Not present  Present
Biopsy:	
Biopsy:	 Yes  No
Results:	 Benign  Malignant
Specify:	 NSCLC  SCLC  Squamous  Non-Squamous
CAML (Cancer-Associated Macrophage-Like Cells) testing results:	
CAML Date:	-----
CAML cells present?	 Present  Absent
CAML size	----- (microns)
CAML number	----- (numeric field)

Confidential

Page 6 of 6

CAML Comments

(free text field)

CTCs present?

Present Absent

CTC number

(numeric field)

Apoptotic CTC

(numeric field)

EMT CTC

(numeric field)

CEVC present?

Present Absent

CEVC number

(numeric field)
